4.0 STUDY TREATMENT

4.1 NIDA Drug Supply Provision of Cannabis Product

We will be administering three cannabis doses to each participant using the vaporizer, including varying concentrations of CBD (low, medium, high): a) 2 vials of 0.01% CBD + 1.9% THC, b) 1 vial of 0.01% CBD + 1.9% THC and 1 vial of 5.1% CBD + 1.4% THC, and c) 2 vials of 5.1% CBD + 1.4% THC.

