4.2 Cannabis Administration Protocol

Participants will receive vaporized cannabis using Volcano vaporizers (Storz and Bickel) with the aforementioned concentrations of CBD and THC at each of three visits. Allocation assignment of visits will be assigned using randomization schedule prepared by our statistician. The allocation schedule will be kept in the pharmacy and concealed from other study personnel. The cannabis will be stored in a freezer at 20°C until the day before use. At least 12 hours before each session, 800 mg of study cannabis will be thawed. The vaporization session will be performed in a HNRP negative pressure room designed to prevent the vapor from being transferred to rooms in which other occupants of the building are working. Puffs from the vaporizer balloon will be standardized so that a consistent amount is inhaled. This will be done according to a cued-smoking procedure shown to produce reliable increases in plasma THC levels⁶⁵. A nurse will provide instructions to participants to 'inhale' (5 seconds), 'hold smoke in lungs' (10 seconds), and 'exhale' and to wait before repeating the puff cycle (40 seconds). Each participant will inhale 4 puffs at each session, an amount that was well tolerated during our previous human laboratory experiments⁶⁰. We will measure vital signs (heart rate, respiration), pain intensity measured by a 0 to 10 numerical rating scale, and HRV at baseline (30 minutes before cannabis administration), at time zero (immediately after cannabis administration), and at 60, 120, and 180 minutes after drug administration. As a secondary measure of pain relief, we will use the Patient Global Impression of Change (PGIC) that will be measured hourly following administration of study medications. We will also conduct a von Frey assessment. The von Frey tool consists of monofilaments that are applied to the skin until bending of the filament occurs, calibrated to a specific pressure and designed to minimize movement artifacts⁶⁶. Increased pain to von Frey stimulation occurs in NP and clinical trials indicate that cannabis treatment can reduce allodynia on this test⁶⁷. We will include this measure in our battery and assess pain using the VAS as previously reported⁶⁷; the von Frey filament will be applied on the dorsum of the more painful foot until bending is observed for 3 seconds, followed by a VAS pain rating.

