
Comparison of NIDA-obtained and dispensary-obtained cannabis effects on NP. We will compare the effect of laboratory cannabis administration and IMPACT self-report data on changes in pain (both measured with NPRS) before and after drug exposure. We will assess pain change scores for the laboratory study and IMPACT measured as the difference between

baseline (before drug) and 60 and 120 minutes after drug, time points that correspond with pain reduction in our prior THC work⁶⁰. We will use the following analyses: 1) plot the distribution of the CBD/THC ratio (x-axis) against pain change (y-axis), calculate the slope of pain change scores for both the lab data and IMPACT, and determine if the slopes are similar or significantly different (a mixed effect model that will estimate changes in outcomes/slopes). 2) If the slopes are nonlinear, we will calculate the area under the curve (AUC) – a measure of total pain change – up to a CBD/THC ratio of 10 (our high CBD dose in the lab). 3) It is possible that our IMPACT data show that many participants only use one or two types of cannabis (e.g., with only a single CBD/THC ratio), thus it might be difficult to plot a CBD/THC ratio distribution. In that event, we will classify IMPACT cannabis use into 3 categories (low CBD/THC ratio, < 1; matched CBD/THC 1:1; high CBD/THC ratio, >1, and examine the correlation between the pain change in each category (averaged over the IMPACT study) with the pain change scores we observe for our low, medium, and high CBD laboratory doses. If our findings indicate a higher slope or greater AUC for NIDA cannabis vs. dispensary cannabis, this would suggest less efficacious pain relief from the local cannabis sources. In contrast, a strong correlation between CBD pain change scores for NIDA and dispensary product in one or more CBD/THC ratio categories would support a consistent finding for the effectiveness of different CBD amounts. In summary, either agreement or discrepancy between NIDA and dispensary data would be highly informative and would help guide future policy recommendations for cannabis-based pain treatment.

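### The lab-versus-dispensary AUC is cut off at a CBD/THC ratio of 10, described as the high lab dose, but the listed high-dose product has a ratio of 3.64

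*Combined protocol and SAP*

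**What the plan says.** The relevant text is the part of section 7.2 that compares NIDA-supplied and dispensary cannabis. It has three steps.

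1. Slopes of pain change on the CBD/THC ratio are compared between the laboratory sessions and IMPACT.
2. "If the slopes are nonlinear, we will calculate the area under the curve (AUC") "up to a CBD/THC ratio of 10 (our high CBD dose in the lab").
3. If participants use too few types of product to plot a ratio distribution, "we will classify IMPACT cannabis use into 3 categories": "low CBD/THC ratio, < 1; matched CBD/THC 1:1; high CBD/THC ratio, >1". Pain change in each category is then correlated "with the pain change scores we observe for our low, medium, and high CBD laboratory doses".

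The section reads a steeper slope or larger AUC for NIDA cannabis as a sign that local products relieve pain less well.

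The laboratory products are listed identically in the Schema, section 2.0 and section 4.1. The high dose is "c) 2 vials of 5.1% CBD + 1.4% THC". The medium dose is "1 vial of 0.01% CBD + 1.9% THC and 1 vial of 5.1% CBD + 1.4% THC". The low dose is two vials of the 0.01% CBD, 1.9% THC product. Section 4.2 adds: "At least 12 hours before each session, 800 mg of study cannabis will be thawed".

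Section 2.0 places the NIDA-versus-dispensary comparison among the secondary and exploratory analyses.

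**The concern.** The AUC limit is stated twice in one phrase, once as a number and once as a dose, and the two do not agree. An analyst who follows the number must carry the laboratory curve well past its last observed point. An analyst who follows the dose stops much earlier. If the laboratory curve is stopped at its last point and the dispensary curve is run to 10, the two areas cover unequal ranges and cannot be compared.

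Because the plan draws a conclusion about dispensary products from which area is larger, an extrapolated laboratory area could create or hide a difference. The direction cannot be known in advance.

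A related gap affects step 3. The plan does not say which laboratory dose each ratio category is set against. If the pairing follows list order, the matched 1:1 category is compared with the medium dose, whose ratio is probably not 1:1.

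**Working it through.** **Inputs.** Product A: 0.01% CBD, 1.9% THC. Product B: 5.1% CBD, 1.4% THC. Low dose = A + A, medium = A + B, high = B + B (section 4.1; the Schema and section 2.0 agree). Stated limit: 10 (section 7.2).

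**Can 10 be reproduced?** Both vials of the high dose hold the same product, so mass, vial count and puffs cancel:

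- High: (2 × 5.1)/(2 × 1.4) = 5.1/1.4 = 3.64.
- Rounding of the label percentages moves this only from 5.05/1.45 = 3.48 to 5.15/1.35 = 3.81.
- Incorrect combinations do not reach 10 either: 10.2/1.4 = 7.29, 10.2/1.9 = 5.37, 5.1/1.9 = 2.68.
- A ratio of 10 would need 0.51% THC at 5.1% CBD, or 14% CBD at 1.4% THC. Neither is listed.
- The sum of the two CBD percentages, 10.2, is close to 10 but is not a ratio. Whether the figure arose that way is not stated.

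**Axis without laboratory data at a limit of 10.** (10 − 3.64)/10 = 0.636, about 64%. The extrapolation runs to 10/3.64 = 2.7 times the highest observed ratio.

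**Illustration of the effect on the AUC.** The documents give no pain values by ratio, so mean reductions of 1.0, 1.6 and 2.0 points are assumed at ratios 0.005, 1.55 and 3.64. The first two ratios are derived below. The area starts at 0.005.

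| Curve through the three points | AUC to 3.64 | AUC to 10 |
|---|---|---|
| Straight segments, flat after 3.64 | 5.78 | 5.78 + 2.0 × 6.357 = 18.49 |
| Straight segments, last one continued | 5.78 | 5.78 + 6.357 × (2.0 + 3.21)/2 = 22.35 |
| Quadratic | 5.89 | 15.51 |

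The value 3.21 is the last segment carried to 10: slope 0.4/2.094 = 0.191, and 2.0 + 0.191 × 6.357 = 3.21.

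- Up to 3.64 the curves differ by 5.89/5.78 = 1.02, or 2%.
- Up to 10, all three differ by 22.35/15.51 = 1.44, or 44%. The quadratic peaks at a ratio of 4.35 and falls to 0.29 points at 10, which is below the assumed relief at the lowest dose. Without it the spread is 22.35/18.49 = 1.21, or 21%.
- With a middle value of 1.5 instead of 1.6, the AUC to 3.64 is 5.59 to 5.64 (1% spread). To 10 it is 18.31 (flat), 20.18 (quadratic) or 23.13 (continued), a spread of 26%.

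**Ratios for step 3.** If the 800 mg thawed per session is the content of the two vials, and the two vials of a same-product dose are equal, each vial holds 400 mg. Then, in mg CBD over mg THC:

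- Low: 0.08/15.2 = 0.005.
- Medium: (0.04 + 20.4)/(7.6 + 5.6) = 20.44/13.2 = 1.55.
- High: 40.8/11.2 = 3.64.

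None of the three is 1:1, and two fall in the category above 1. For the medium dose to be 1:1, the mass share w of product B must satisfy 5.1w + 0.01(1 − w) = 1.4w + 1.9(1 − w). This gives w = 1.89/5.59 = 0.338, about 270 mg of B and 530 mg of A. If B makes up 25% to 75% of the mass, the medium ratio runs from 0.72 to 2.51.

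**The case against.** The fair counter-argument is that the parenthesis shows the intent: stop at the top laboratory dose. The plan nowhere mentions extrapolation, so 10 may be no more than a slip. That reading is plausible, and under it the damage is confined to one wrong number. The text does not say which half of the phrase governs, however, and an integration limit fixed in advance should have one value.

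The AUC illustration rests on invented pain values, and its widest figure depends on a quadratic that behaves implausibly at high ratios and that the plan does not propose. That criticism stands: the 44% should not be taken as an estimate. Dropping the quadratic still leaves 21% at a limit of 10, against about 2% inside the lab range. The 64% is a length of axis, not a share of observations, since the distribution of dispensary ratios is unknown.

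The step 3 point is weaker. The low, medium and high labels describe CBD content, not ratio class, so a medium dose that is not 1:1 contradicts nothing. The pairing is inferred from list order, and equal vial mass is supported by section 4.2 but not stated. The ratio inhaled at the medium dose may also differ from the ratio loaded, and the plan is inconsistent about puffs: section 4.2 gives both 4 and 8, and section 7.1 labels doses by 4 and 8. What remains is that the pairing is unspecified.

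Finally, the comparison is secondary or exploratory, and steps 2 and 3 run only under stated conditions. That limits the reach of the error but does not remove it.

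**Conclusion.** The limit is wrong as written. The high laboratory dose has a CBD/THC ratio of 3.64 on every listing in the document, and no listed product gives 10. This follows from the stated concentrations alone. Applied literally, the limit leaves about 64% of the 0 to 10 axis without laboratory data, and the laboratory AUC becomes sensitive to an assumed curve shape. The size of that sensitivity (21% to 44% in the illustration, 26% with a slightly different middle value) rests on assumed pain reductions and shows scale only.

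The step 3 mismatch is conditional on list-order pairing and equal vial mass, and the main point does not depend on it.

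The consequence is confined to conditional steps of a secondary or exploratory comparison. The slope comparison, the Aim 1 analyses and the main Aim 2 model are not affected. The plan should be corrected before the comparison is run.

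**What to change.** - Reconcile the ratio of 10 in section 7.2 with the products listed in the Schema, section 2.0 and section 4.1. This review takes no view on which product is intended.
- Compute the AUC for both sources over the same ratio range, namely the one the laboratory products cover. For the products as listed, the upper limit is 3.64. Describe dispensary use above that limit separately.
- State the CBD/THC ratio of each laboratory dose and the vial mass on which it rests.
- For step 3, define the categories so that each laboratory dose is compared with IMPACT use of a similar ratio, and state the pairing.

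The cost is SAP wording. The one drawback is a narrower comparison: dispensary use above the laboratory range is described but not contrasted with laboratory data.

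### Section 7.2 puts the high-CBD laboratory dose at a CBD/THC ratio of 10; the product strengths give 3.64, so most of the planned AUC range has no laboratory data

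*Combined protocol and SAP*

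**What the plan says.** Section 4.1 lists three doses made from two products. The low dose is two vials of 0.01% CBD and 1.9% THC. The medium dose is "b) 1 vial of 0.01% CBD + 1.9% THC and 1 vial of 5.1% CBD + 1.4% THC". The high dose is "c) 2 vials of 5.1% CBD + 1.4% THC". The Schema and section 2.0 give the same compositions.

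The NIDA-versus-dispensary comparison in section 7.2 has three steps:

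1. The analyst is to "plot the distribution of the CBD/THC ratio (x-axis) against pain change (y-axis") and compare the slopes from the laboratory and IMPACT.
2. If the relation is nonlinear, an AUC replaces the slope, taken "up to a CBD/THC ratio of 10 (our high CBD dose in the lab").
3. If the ratios in IMPACT are too few to plot, dispensary use is sorted into below 1, "matched CBD/THC 1:1; high CBD/THC ratio, >1". Pain change in each category is then correlated "with the pain change scores we observe for our low, medium, and high CBD laboratory doses".

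A conclusion is fixed in advance. If the slope or AUC is greater for NIDA cannabis, "this would suggest less efficacious pain relief from the local cannabis sources". Agreement or discrepancy alike "would help guide future policy recommendations for cannabis-based pain treatment".

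**The concern.** The AUC limit is justified by the laboratory's highest dose, yet the figure given for it does not match that dose. If the AUC step is triggered and the numeral is followed, the laboratory curve has to be carried well past its last observed point. The plan does not say how. The comparison would then partly reflect the method of extension and not the two sources of cannabis, while its reading is already tied to a statement about the efficacy of dispensary products.

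Step 3 has a similar difficulty. It sets three ratio categories against three laboratory doses, but the doses do not appear to fall one in each category.

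**Working it through.** **Inputs.** Product strengths are from section 4.1: 0.01% CBD with 1.9% THC, and 5.1% CBD with 1.4% THC. The limit of 10 and the categories are from section 7.2. Mass per vial is not stated, and equal mass is assumed where it matters.

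**Ratio of each dose** = total CBD / total THC.

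| Dose | Calculation | Ratio |
|---|---|---|
| Low | 0.02 / 3.8 | 0.005 |
| Medium (equal vials) | (0.01 + 5.1) / (1.9 + 1.4) = 5.11 / 3.30 | 1.55 |
| High | 10.2 / 2.8 = 5.1 / 1.4 | 3.64 |

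Both vials of the high dose are the same, so vial mass and number of puffs cancel and 3.64 needs no assumption beyond the stated strengths. Any mix of the two products lies between 0.005 and 3.64.

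**Attempts to reproduce 10.** Doubling CBD but not THC gives 10.2/1.4 = 7.29. Using the other product's THC gives 10.2/1.9 = 5.37 or 5.1/1.9 = 2.68. Rounding of the strengths allows 5.05/1.45 = 3.48 to 5.15/1.35 = 3.81. None reaches 10. The summed CBD strength, 2 × 5.1 = 10.2, is close, but it is not a ratio, and the plan does not say where 10 comes from.

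**Range without laboratory data.** (10 − 3.64)/10 = 64%, and 10/3.64 = 2.75.

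**Effect on the AUC.** Suppose both sources follow one identical curve, so the correct NIDA/dispensary AUC ratio is 1. Suppose also that the analyst plots the high dose at 10 and applies the trapezoid rule to the laboratory points. The curve shapes are assumptions, since the documents give none.

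- Saturating, r/(r+4). Laboratory values are 0.001, 0.279 and 0.477. Trapezoid area: 1.543 × 0.140 + 8.452 × 0.378 = 3.41. True area to 10: 4.99. Ratio about 0.7.
- Declining, 1/(1+r/4). Laboratory values are 0.999, 0.721 and 0.523. Trapezoid area: 1.543 × 0.860 + 8.452 × 0.622 = 6.58. True area: 5.01. Ratio about 1.3.
- Same method, other shapes: flat gives 1.0; 1 + r/(r+k) with k from 0.5 to 4 gives about 0.9; the hump r·exp(−r/3) gives 1.21.

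The error can therefore go either way.

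**Effect on the step 1 slope.** With the doses plotted at their own ratios there is no distortion. With the high dose at 10, x = (0.005, 1.55, 10) against a response linear in (0.005, 1.55, 3.64) gives Sxy/Sxx = 18.79/57.90 = 0.32 of the true slope.

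**Step 3 categories.** The low dose (0.005) is below 1; the medium (1.55) and high (3.64) doses are both above 1; no dose is at 1:1. The medium dose would be exactly 1:1 only if the low-CBD vial made up 3.70/(3.70 + 1.89) = 66% of the mass. With that vial at 60% or 40% of the mass, the ratio is 1.20 or 1.91. If the puff labels in section 7.1 meant that the medium dose is the 5.1% vial alone, its ratio would be 3.64, which is not 1:1 either.

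**The case against.** The strongest reply is that this is a one-number slip whose intent can still be read. The words in parentheses tie the limit to the highest laboratory dose, so the rule is to stop where the laboratory data stop, and an analyst working from section 4.1 would find 3.64 at once. That is a fair reading of intent, but it does not make the written limit right, and correcting it costs very little.

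The second reply concerns size. The distortions above depend on assumed curves and on one way of handling the gap, and the plan specifies neither. This stands, and the figures are illustrations only. A reader might infer that the error always makes NIDA cannabis look weaker, so that a real dispensary deficit would be missed. The documents do not support that, because they do not fix the curve shape, and declining or humped curves give the opposite error. Nor do they support quoting an extrapolated quadratic in the ratio, which the plan never proposes.

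The third reply is that section 7.2 does not expressly pair the medium dose with the 1:1 category, and that vial mass is not given. Both are true. The pairing is inferred from the order of the two lists, and 1.55 assumes equal vials.

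Finally, section 2.0 places this comparison among the secondary and exploratory analyses, and steps 2 and 3 are each conditional. That limits the importance of the point.

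**Conclusion.** The limit of 10 is wrong as written. The high-CBD dose has a ratio of 3.64, on the stated strengths alone, and 64% of the planned range has no laboratory data. If the AUC step is reached, its result depends on an unstated choice about that gap, with error possible in either direction. The step 3 mismatch also holds, provided that vials are of equal mass and the categories pair with the doses in list order.

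The severity is minor. A reader might infer that the trial's main dose comparison is compromised. It is not: Aim 1 treats dose as categorical and never uses the ratio, so section 7.1 needs no change. Step 1 is also sound if the doses are plotted at their actual ratios.

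**What to change.** All changes are in the NIDA-versus-dispensary part of section 7.2:

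- **Step 1:** plot the laboratory doses at 0.005, 1.55 and 3.64, and state the vial mass behind the middle value.
- **Step 2:** replace 10 with 3.64. Compute both AUCs over 0.005 to 3.64, evaluating both curves at the three laboratory ratios with the same trapezoid rule. Identical curves then give a ratio of exactly 1.
- **Step 3:** state which dose each category is set against. Use cut-points midway between the laboratory ratios: (0.005 + 1.55)/2 = 0.78 and (1.55 + 3.64)/2 = 2.6, given equal vial mass. Limit the top category to 2.6 to 3.64 for the main comparison.
- **Above 3.64:** report dispensary events separately, with no laboratory comparison.

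The cost is that dispensary events above 3.64 leave the direct comparison and the top category may be sparse; the documents do not say how many events this affects. Products, sample size, randomisation and the Aim 1 model stay as they are.

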7.2 Aim 2 Measures and Analyses

Based on our existing data for PLWH SMS compliance, we anticipate that participants will respond to 80-90% of the daily text messages during IMPACT. To address the issue of missing data, we will incorporate questions that allow participants to indicate their pain and cannabis use for the prior day if they did not respond to the earlier message. For days that have completely missing data, we will treat the intermittently missing data as missing completely at random. However, this assumption will be checked in sensitivity analyses by comparing the outcomes of participants based on the amount of missing data. Study dropout will be examined separately using statistical methods in current use [Diggle, Heagerty, Liang, and Zeger, *Analysis of Longitudinal Data*, 2nd ed., Oxford University Press, 2013]: The relationship between CBD, THC, and the CBD/THC ratio during a cannabis exposure event to changes in pain before and after the event will be examined using longitudinal data methods – e.g., mixed-effects linear models, controlling for potential confounders including baseline pain, in addition to those listed under Aim 1. The total CBD and THC consumed during the exposure will be calculated using the SUI method, estimating total grams of cannabis consumed multiplied by the percentages of CBD and THC content. Subject-specific random intercepts will be included in the model in order to account for the within-subject correlation of the outcome. Exploratory analyses will examine if there are different effects of reported cannabis strain (Sativa, Indica), individual types (e.g., OG Kush, Sour Lemon, etc.), or mode (smoking, vaporizing, ingesting food product) on pre-post changes in NP. We will also conduct exploratory analyses to examine if there is an interaction between reported levels of THC (low, < 1%, medium, 1-6%, high, > 10%) and CBD (low, < 1%, medium, 1-6%, high, > 10%) on pain change after drug use. The association of daily measures of pain levels with HRV will use a linear mixed-effects model, adjusting for potential confounders. The within-subject correlation will be accounted for using subject-specific random intercepts. Longitudinal changes in HRV between the first and last week will be assessed with a linear model that includes cannabis use (light vs. heavy) and CBD/THC intake, as predictors. Regression analyses will also examine the association between HRV and self-report pain measures quantified at the baseline and final visits.

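### When the relation is linear, the NIDA-versus-dispensary comparison infers pain-relief efficacy from a slope on the CBD/THC ratio, and a slope does not measure how much relief is obtained

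*Combined protocol and SAP*

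**What the plan says.** The comparison is at the end of section 7.2 (Aim 2). The outcome is the NPRS change between "baseline (before drug) and 60 and 120 minutes after drug", in the laboratory and in IMPACT. Three analyses follow.

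- The first is to "plot the distribution of the CBD/THC ratio (x-axis) against pain change (y-axis), calculate the slope of pain change scores" for both sources and test whether the slopes differ, using "a mixed effect model that will estimate changes in outcomes/slopes".
- The second is conditional: "If the slopes are nonlinear, we will calculate the area under the curve (AUC"), described as total pain change, taken "up to a CBD/THC ratio of 10 (our high CBD dose in the lab").
- The third is a fallback if participants use only one or two products: a correlation of pain change within three ratio categories.

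The interpretation is then fixed: "If our findings indicate a higher slope or greater AUC for NIDA cannabis vs. dispensary cannabis, this would suggest less efficacious pain relief" from local sources. The section adds that either agreement or discrepancy would help guide policy recommendations.

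No covariates are named for this comparison, and the direction of subtraction in the change score is not given. Earlier in section 7.2, the IMPACT event model controls for baseline pain and the Aim 1 confounders, uses CBD, THC and their ratio as predictors, and explores "mode (smoking, vaporizing, ingesting food product"). Section 2.0 lists the NIDA-versus-dispensary comparison among secondary and exploratory analyses.

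**The concern.** A regression of relief on the ratio has an intercept and a slope, and how much relief a source gives depends on both. A rule that looks only at the slope can fail in two ways. It can favour the source with the steeper line although the other gives more relief throughout the observed range. It can also find no difference when one source is worse by a constant amount.

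Because the sign of change is undefined, even the direction of a higher slope is unclear. If change is post minus pre, a numerically higher slope means relief grows less with the ratio.

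At stake is a published statement that dispensary products relieve pain less, or no worse, than NIDA product, based on a quantity that does not measure relief. The plan expects the comparison to inform policy, so the inference should match the estimand.

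**Working it through.** **Inputs.** Vial contents are from section 4.1: low, 2 × (0.01% CBD + 1.9% THC); medium, one of those plus one of (5.1% CBD + 1.4% THC); high, 2 × (5.1% CBD + 1.4% THC). Equal vial weights are assumed.

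**1. The plan's own figure.** Ratio = summed CBD% / summed THC%.
- Low: 0.02/3.8 = 0.005
- Medium: 5.11/3.3 = 1.55
- High: 10.2/2.8 = 5.1/1.4 = 3.64

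The stated ratio of 10 does not reproduce. Mixed forms also miss it: 10.2/1.4 = 7.29, 10.2/1.9 = 5.37, 5.1/1.9 = 2.68. With these vials, (10 − 3.64)/10 = 64% of the AUC range lies beyond any laboratory observation. No power is stated for this comparison.

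**2. Can the slope rule reverse?** Assumed lines, in NPRS points of relief (positive = better): laboratory 1.0 + 0.3r, dispensary 2.5 + 0.1r. Dispensary minus laboratory = 1.5 − 0.2r.

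| r | Laboratory | Dispensary | Difference |
|---|---|---|---|
| 0.005 | 1.00 | 2.50 | 1.50 |
| 1.55 | 1.46 | 2.65 | 1.19 |
| 3.64 | 2.09 | 2.86 | 0.77 |

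The slopes are 0.3 and 0.1, so the rule calls dispensary products less efficacious. The lines cross at 1.5/0.2 = 7.5, above the laboratory range.

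**3. Does the AUC reverse too?** AUC = a·u + b·u²/2. To u = 10: laboratory 10 + 15 = 25, dispensary 25 + 5 = 30. It ranks the sources correctly here, but the plan would not calculate it, because both lines are straight.

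**4. How often?** There were 1,000 simulations of 100 participants × 3 laboratory doses and 80 × 52 IMPACT events (the section 7.4 numbers). Assumptions: between-subject SD 1.2, residual SD 1.5, IMPACT ratios uniform on 0 to 3.64, sources simulated independently, and per-person slopes compared by a Welch test at two-sided 5%.
- Laboratory 1 + 0.25r, dispensary 2.5 + 0.05r (the same differences as step 2): mean dispensary relief was greater in 100% of runs, and the rule called it less efficacious in 91%.
- Dispensary flat at 3.0: the rule called it less efficacious in 98%.
- Equal slopes of 0.25, dispensary 1 point lower throughout: flagged in 2%.

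**5. What else moves the slope?**
- Amount: assume 0.03 points per mg CBD in both sources and 800 mg split equally between vials (0.08, 20.44 and 40.8 mg CBD). The fitted slope per ratio unit is 0.33 at the laboratory amount, 0.17 at half and 0.67 at double.
- Pre-dose pain: assume relief rises by 6% of pre-dose pain per ratio unit. The slope is 0.06 × 4 = 0.24 at NPRS 4 and 0.06 × 7 = 0.42 at NPRS 7.

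**6. Can laboratory CBD and THC amounts be separated?** Summed CBD is 0.02, 5.11, 10.2 (steps +5.09, +5.09). Summed THC is 3.8, 3.3, 2.8 (steps −0.5, −0.5). They are exactly collinear. THC also falls by 1.0/3.8 = 26% across the laboratory slope, so the ratio is not a pure CBD effect.

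**The case against.** The strongest reply has five parts.

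- **The rule also names the AUC, which carries level, and the mixed model is said to estimate outcomes as well as slopes.** This stands in part. The fault is confined to the linear branch, where the AUC is not calculated and the written interpretation rests on the slope.
- **The example is invented and depends on range.** This stands. Beyond a ratio of 7.5 the laboratory line is higher (4.0 against 3.5 at 10). The example shows that the rule can fail where laboratory data exist, not that it will.
- **A reader might infer that amount, route and pre-dose pain are left unadjusted.** The documents do not support that. The IMPACT event model in section 7.2 controls for baseline pain, has CBD and THC as predictors and explores mode, and the comparison's outcome is already a change score. What is missing is a statement that any of this carries into the two-source comparison. The Aim 1 list covers mode of prior use, not the route of the event.
- **The same participants contribute to both sources.** The abstract says so, and this limits stable between-person confounding. It does not turn a slope into a level of relief.
- **The stakes are modest.** Section 2.0 calls the comparison secondary and exploratory, and the wording is hedged. This bears on severity, not on whether the inference is valid.

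**Conclusion.** The point holds for the linear branch. There, a slope difference is read as an efficacy difference, and the rule can reverse or miss the true difference in relief. The size is illustrative: dispensary products better by 0.77 to 1.50 NPRS points within the laboratory range yet judged worse, in 91% of simulated trials under the assumed lines and variances. These are not estimates for this trial.

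Two faults need no assumed effects. The sign of the change score is undefined. The AUC limit of 10 also disagrees with the section 4.1 vials (3.64 at the high dose, where two identical vials give that ratio whatever their weights), and these passages must be reconciled.

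Three stronger readings are not supported: that reversal is inevitable, that the AUC shares the slope's fault, and that the plan ignores confounding altogether. The change should be made before the comparison is run, but the Aim 1 dose comparisons do not depend on it.

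**What to change.** 1. Delete the efficacy inference from slope. Report a slope difference only as a difference in ratio dependence.
2. Fit one joint mixed model with source, ratio and source × ratio, and participant random effects. Report mean pain change by source at 60 and 120 minutes, and the difference with a confidence interval, at common ratios within the range the laboratory doses cover (0.005 to 3.64 from the stated vials, equal weights assumed). Allow curvature in the ratio if the data require it.
3. Define the sign of the change score. Reconcile the ratio of 10 with the vial contents, and end the AUC at the highest ratio the laboratory doses cover.
4. State that the section 7.2 baseline-pain adjustment applies in the joint model, and define it as the same pre-dose rating in both sources.
5. Restrict the main comparison to inhaled events. This still pools smoking with vaporizing, whereas the laboratory only vaporizes.
6. Do not require separate laboratory CBD and THC amount covariates, which are collinear across the three doses. Treat amount as a sensitivity analysis, once the 4-puff and 8-puff statements in section 4.2 have been reconciled.
7. Present the result as exploratory. Blinded laboratory dosing and open-label, self-selected use still differ, and covariates cannot remove that.

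**Cost:** mainly SAP wording, with no new visits. The plan already provides for recording route and pain around each event. The inhaled-only restriction leaves fewer IMPACT observations, and the sensitivity analysis must wait for the puff reconciliation.
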